6.3 Stent thrombosis

Probable/definite stent thrombosis will be defined according the Academic Research Consortium definition⁴². With regard to the primary endpoint of the study, the adjudication will follow a hierarchical order with death first, MI second and stent thrombosis third, mostly in the case of recurrent ischemia without enzyme elevation.

6.4 Bleeding Classification

All bleeding events will be considered in patients undergoing cardiac and non cardiac surgery.

Bleeding events will be classified according to BARC classification.

Bleeding Academic Research Consortium Definition for Bleeding (Ref 43)

- Type 0: no bleeding
- Type 1: bleeding that is not actionable and does not cause the patient to seek unscheduled performance of studies, hospitalization, or treatment by a healthcare professional; may include episodes leading to self-discontinuation of medical therapy by the patient without consulting a healthcare professional

- Type 2: any overt, actionable sign of hemorrhage (eg, more bleeding than would be expected for a clinical circumstance, including bleeding found by imaging alone) that does not fit the criteria for type 3, 4, or 5 but does meet at least one of the following criteria: (1) requiring nonsurgical, medical intervention by a healthcare professional, (2) leading to hospitalization or increased level of care, or (3) prompting evaluation

- Type 3

Type 3a: overt bleeding plus hemoglobin drop of 3 to <5 g/dL* (provided hemoglobin drop is related to bleed); any transfusion with overt bleeding

Type 3b: overt bleeding plus hemoglobin drop ≥ 5 g/dL* (provided haemoglobin drop is related to bleed); cardiac tamponade; bleeding requiring surgical intervention for control (excluding dental/nasal/skin/hemorrhoid); bleeding requiring intravenous vasoactive agents

Type 3c: intracranial hemorrhage (does not include microbleeds or hemorrhagic transformation, does include intraspinal); subcategories confirmed by autopsy or imaging or lumbar puncture; intraocular bleed compromising vision

- Type 4: CABG-related bleeding, including perioperative intracranial bleeding within 48 h, reoperation after closure of sternotomy for the purpose of controlling bleeding, transfusion of >5 U whole blood or packed red blood cells within a 48-h period, chest tube output >2L within a 24-h period
- Type 5: fatal bleeding

Type 5a: Probable fatal bleeding; no autopsy or imaging confirmation but clinically suspicious

Type 5b: Definite fatal bleeding; overt bleeding or autopsy or imaging confirmation

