4.3 Secondary endpoints

Patients undergoing non cardiac surgery:

- The composite of death, myocardial infarction, probable/definite stent thrombosis according the Academic Research Consortium definition⁴⁴ and bleeding events of Bleeding Academic Research Consortium (BARC) grade ≥ 3 at 30 days
- The composite of death, myocardial infarction and probable/definite stent at 30 days
- The incidence of bleeding events of Bleeding Academic Research Consortium (BARC) grade ≥ 3 at 30 days
- The type and the length of discontinuation of any antiplatelet therapy in patients undergoing non cardiac surgery according to time from PCI to surgery
- Rate of non cardiac surgical procedures within 12 months from PCI divided into quartiles (0-3, 3-6, 6-9, 9-12 months)
- Delay in performing non cardiac surgical procedure

Patients undergoing cardiac surgery:

- The composite of death, myocardial infarction, probable/definite stent thrombosis according the Academic Research Consortium definition⁴⁴ and bleeding events of Bleeding Academic Research Consortium (BARC) grade ≥ 4 at 30 days
- The composite of death, myocardial infarction and probable/definite stent at 30 days
- The incidence of bleeding events of Bleeding Academic Research Consortium (BARC) grade ≥ 4 at 30 days
- The type and the length of discontinuation of any antiplatelet therapy in patients undergoing cardiac surgery according to time from PCI to surgery
- Rate of cardiac surgical procedures within 12 months from PCI divided into quartiles (0-3, 3-6, 6-9, 9-12 months)
- Delay in performing cardiac surgical procedure

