6.3 Myocardial Infarction

All definite MIs will be counted as events whether they occurred spontaneously or as the direct consequences of a procedure or operation.

The definition of perioperative MI includes cardiac marker evidence of MI with either troponin or CK-MB elevation greater than the ULN with a typical rise and fall⁴⁴ and 1 or more of the following defining features⁴⁵:

- ischemic symptoms (such as chest, epigastric, arm, wrist, or jaw discomfort or shortness of breath),
- development of pathologic Q waves in 2 contiguous leads during ECG,
- ischemic changes detected with ECG (new or presumed-new ST-segment elevation or depression or T-wave inversion in at least 2 contiguous leads during ECG),
- coronary artery intervention (such as percutaneous coronary intervention or coronary artery bypass graft surgery),
- or evidence of MI on cardiac imaging (a new or presumed-new cardiac wall-motion abnormality on echocardiographic imaging or a new or presumed-new fixed defect on radionuclide imaging).
- a patient's autopsy findings demonstrated acute MI.

According to the 3rd Universal Definition of MI⁴⁴,

- following PCI, CK-MB elevation must be $>5 \times$ ULN.
- Following CABG, the definition for an MI requires that cardiac markers are $>10 \times$ ULN.

Outcome adjudicators evaluated all potential MIs, and their decisions will be used in the statistical analyses. The event adjudication committee should also consider the clinical features (eg, renal insufficiency), possible alternative diagnoses (eg, pericarditis), pattern of marker release (eg, absence of a rise and fall), and known sensitivity/specificity of the various cardiac markers in the adjudication of infarction, particularly when there is discordance in the results of multiple markers.

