7.2 Description of Statistical Methods

Continuous numeric variables will report as means with SD and compared using the Student’s t- or Wilcoxon rank-sum test. Categorical variables will be presented as counts and percentages and will be compared using the chi-square or Fisher’s exact test. To examine the effect of significant factors on two different groups (Group 1 vs Group 2) the hazard ratio of the interaction term will be calculated. To identify the independent predictors for in hospital NACE, 30day MACE and 30-day BARC bleedings, first univariate and then multivariate logistic regression models will apply. The BARC bleedings will be considered according to type of surgery. Specifically, BARC bleedings grade ≥ 3 will be considered in patients undergoing cardiac surgery, and BARC bleedings grade ≥ 4 will be taken into account for non-cardiac surgery. Covariates for multivariable models will be selected on the basis of a backward stepwise algorithm in a Cox proportional hazards model. Additionally, to minimise group differences on confounding covariates between patients who will be managed with consensus document (group 1) and those who will be received local practice (group 2), a 1:2 propensity score matching would be used. Propensity scores will be calculated with logistic regression, with multiple imputation and backwards elimination with a significance level to stay of 0.05. To ensure that the comparison between two groups (group 1 vs group 2) would not be bias, the proportion of patients who will not received consensus document within center that traditionally used it, will be excluded. The results will be presented as ORs with 95% confidence intervals (CI) and p values. For all

analyses, a two-sided $P <0.05$ will be required for statistical significance. All data will be analyzed using the Statistical Package of Social Sciences version 20 (IBM SPSS, Chicago, IL).

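### Under section 4.3, non-fatal major bleeding after non-CABG cardiac surgery is not counted; section 7.2 contradicts that threshold, and the raised MI marker threshold is stated for CABG only

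*Combined protocol and SAP*

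**What the plan says.** **Endpoints.** Section 4.3 lists, for patients having cardiac surgery, "The incidence of bleeding events of Bleeding Academic Research Consortium (BARC) grade ≥ 4 at 30 days", and uses the same grade in the first composite, together with death, MI and stent thrombosis.

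**Bleeding grades.** Section 6.4 lists "Type 4: CABG-related bleeding". Its criteria are early intracranial bleeding, re-opening of the sternotomy to control bleeding, large transfusion and high chest-tube loss. Type 5 is fatal bleeding. Type 3b includes cardiac tamponade and "bleeding requiring surgical intervention for control (excluding dental/nasal/skin/hemorrhoid"). Type 3c is intracranial bleeding.

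**Statistics section.** Section 7.2 states the reverse assignment. Its rule for the cardiac group is "BARC bleedings grade ≥ 3 will be considered in patients undergoing cardiac surgery". Non-cardiac operations are given grade 4 or higher there.

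**MI.** Section 6.3 (Myocardial Infarction) requires troponin or CK-MB above the ULN with a typical rise and fall, plus at least one defining feature; adjudicated decisions enter the analysis. It then adds: "Following CABG, the definition for an MI requires that cardiac markers are" more than 10 × ULN. No corresponding line covers other cardiac operations.

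**Population.** Section 4.4.1 admits stented patients having any kind of surgery. No section limits cardiac surgery to CABG.

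**The concern.** The cardiac-surgery endpoints apply to every cardiac operation, but two of the rules that decide whether an event counts are written for CABG alone. For bleeding, a grade 4 threshold with a CABG-related type 4 leaves only fatal bleeding to count after, say, isolated valve surgery. For MI, the marker threshold after such surgery is lower than after CABG.

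The registry compares groups of centers (section 4.1) without randomization, so the mix of cardiac operations can differ between them. If it does, part of any difference in the cardiac bleeding and composite endpoints would come from which operations were performed, on top of any effect of antiplatelet management. Even with an identical mix, serious non-fatal bleeding would go uncounted in one class of patients. That matters in a study whose rationale is the balance between ischemia and bleeding.

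**Working it through.** The plan gives no figure to reproduce here. The sample size in section 7.1 is stated without event rates and does not bear on these definitions. The check is to map the thresholds onto the definitions and then size the effect under stated assumptions.

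**Step 1: bleeding, read literally.**

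| Event | Type after CABG | Type after other cardiac surgery | Counts under 4.3 (≥4): CABG / other | Counts under 7.2 (≥3): CABG / other |
|---|---|---|---|---|
| Re-opening of the sternotomy for bleeding | 4 | 3b | yes / no | yes / yes |
| Intracranial bleeding within 48 h | 4 | 3c | yes / no | yes / yes |
| More than 5 U red cells in 48 h with overt bleeding | 4 | at least 3a | yes / no | yes / yes |
| Fatal bleeding | 5 | 5 | yes / yes | yes / yes |

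Tamponade is listed under 3b. After non-CABG surgery it stays below grade 4 even if the chest is re-opened; after CABG the re-opening itself meets type 4.

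Two consequences follow.
- Under 4.3, the bleeding component adds nothing to the first composite after non-CABG cardiac surgery. The only bleeding that counts is fatal, and death is already a component. For these patients the first composite equals the second.
- Under 7.2, the fatal-only result moves to non-cardiac surgery: with a grade 4 threshold and no CABG, only type 5 can count there.

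**Step 2: MI.**

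| Requirement | After CABG | After other cardiac surgery |
|---|---|---|
| Marker | >10 × ULN | >1 × ULN |
| Typical rise and fall | general rule | general rule |
| At least one defining feature | yes; coronary intervention, including CABG, is on the list | yes |
| Adjudication | yes | yes |

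Only the marker line differs in writing.

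**Step 3: size of the bleeding effect.** The documents give no CABG share and no cardiac bleeding rates. Assume, in both center groups and for every cardiac operation, that 10% of patients meet the type 4 criteria or die of bleeding, and that 1% die of bleeding. With CABG share *s*, the rate recorded under 4.3 is

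R(s) = 10% × s + 1% × (1 − s) = 1% + 9% × s.

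The spurious difference between groups is 9 points × (difference in s).

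| Gap in CABG share | Spurious difference | Example |
|---|---|---|
| 0 | 0 | equal shares |
| 5 points | 9 × 0.05 = 0.45 points | |
| 10 points | 9 × 0.10 = 0.9 points | 60% vs 70%: 6.4% vs 7.3% |
| 30 points | 9 × 0.30 = 2.7 points | 50% vs 80%: 5.5% vs 8.2% |

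At equal shares no bias arises between groups, but events are still lost: at 50% CABG in both, 5.5% is recorded where 10% would meet the criteria.

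The effect on MI cannot be sized, because the documents give no marker distribution or MI rate after either type of surgery.

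**The case against.** The case against has several parts.

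- **The bleeding problem depends on which section governs.** Under the threshold in 7.2, re-opening after valve surgery counts. This stands: the conclusion is conditional on 4.3. But 4.3 is the endpoint list, and nothing says that 7.2 overrides it.
- **The events are recorded anyway.** Section 4.5.3 captures major bleeding, transfusions and reoperation due to bleeding in everyone, and 6.4 says all bleeding will be considered. So the data can be reported by BARC type. This limits the harm, but does not change what the named endpoint counts.
- **Adjudicators might extend type 4 themselves.** Its criteria could be met after any sternotomy. The text, however, labels them CABG-related and gives no instruction to extend them.
- **Section 7.2 plans matching and multivariable models.** True, but it names no covariates and uses backward elimination, so balance on operation type is not assured. Adjustment also cannot restore events that were never counted.

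Stronger readings are tempting. A reader might infer that MI after non-CABG surgery is counted at any marker above the ULN; the text also requires rise and fall, a defining feature and adjudication. A reader might infer that the MI rule is far looser than for CABG. That is not shown: read literally, CABG may itself supply the defining feature, while a valve patient needs other evidence. The tenfold ratio describes one criterion, not the MI rate.

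**Conclusion.** The point holds in a limited form. If section 4.3 governs, non-fatal major bleeding after non-CABG cardiac surgery drops out of the cardiac bleeding endpoint and the first composite, while the same re-opening after CABG is counted. If 7.2 governs, this does not arise for cardiac surgery. The MI gap is independent of that conflict: no raised marker threshold is stated for other cardiac surgery, and the general rule applies.

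The size is unknown. Under the assumed 10% and 1%, the spurious difference in recorded bleeding runs from none at equal CABG shares to 0.45, 0.9 and 2.7 points at gaps of 5, 10 and 30 points. None of these gaps is supported by the documents over the others.

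Two broader conclusions are not supported. The cardiac endpoints are not CABG-only as a whole: only type 4 and the 10 × ULN line are CABG-specific, while death, stent thrombosis, type 5 and the general MI definition apply to all. Nor do the rates reflect CABG share instead of antiplatelet management; case mix is an added influence. All affected endpoints are secondary; the primary endpoint, antiplatelet discontinuation, is untouched. The change is still worth making, because it is cheap and the rule as written misses events that the endpoint is meant to capture.

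**What to change.** 1. Reconcile sections 4.3 and 7.2, so that one bleeding threshold is stated for cardiac and one for non-cardiac surgery. Check that a grade 4 threshold is not left on non-cardiac surgery by oversight.
2. If grade 4 or higher is kept for cardiac surgery, state in 6.4 that the type 4 criteria apply to every cardiac operation, and label this as an adaptation of BARC.
3. Name CABG versus non-CABG as a covariate in the propensity score and in the models for the cardiac endpoints, and retain it regardless of backward elimination.
4. State in 6.3 which marker rule adjudicators apply to MI after non-CABG cardiac surgery. The choice of threshold belongs to the steering committee; the point is that it be written down.

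The cost is a few sentences in the protocol and matching text for the event-adjudication committee. Reoperation for bleeding and transfusions are already collected; chest-tube output is not listed in 4.5.3, so confirm that the eCRF or uploaded source documents supply it. The downside is that the cardiac bleeding endpoint is no longer standard BARC. Reporting the unmodified BARC types alongside would preserve comparability with other studies.

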6.5 Rate of non cardiac surgical procedures within 12 months from PCI

The rate of cardiac and non cardiac surgical procedures performed within 12 months from PCI will be assessed. Time from PCI to surgery will be divided into 4 quartiles: from 0 to 3 months, from 3 to 6 months, from 6 to 9, and from 9 to 12 months.

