Cardiologists defined the thrombotic risk based on a series of clinical features and procedural characteristics. In particular, the definition of thrombotic risk (low, intermediate or high) was derived after careful revision of the literature which led to the formulation of a tables which summarized the information obtained. All Cardiology members of the Writing Committee provided their feedback until a consensus was reached. Surgeons classified all interventions according to the inherent hemorrhagic risk (low, intermediate, or high) of each specific surgery. In particular, bleeding risk was not solely based on the amount of blood loss, but mostly according to the anticipated difficulty in achieving adequate local hemostasis. The bleeding risk was defined in a total of about 250 surgical procedures. Finally, the most appropriate antithrombotic treatment regimen in the perioperative phase was defined for each procedure taking into consideration both the thrombotic and bleeding risk profiles. Ultimately, a consensus agreement was reached which involved not only cardiologists and surgeons, but also anesthesiologists and hematologists. Importantly, the recommended antithrombotic treatment regimen was not standard to a given thrombotic/bleeding risk profile, but was specific to each individual surgical specialty.

In general, if surgery cannot be delayed, it should be performed after the first month and ideally after at least 3 months from PCI [25, 32, 46, 49]. The vast majority of procedures may be performed while on aspirin, with the possible exception of surgeries at extremely high risk of bleeding (e.g., neurosurgery). When a wash-out of P2Y12 inhibiting therapy is required, this should be performed judiciously according to the timing of surgery: 5 days for clopidogrel and ticagrelor and 7 days for prasugrel. Recent data from a large observational study in CABG patients demonstrated that discontinuation 3 days before surgery, as opposed to 5 days, did not increase the incidence of major bleeding complications with ticagrelor (OR 0.93 (95% CI 0.53-1.64), p=0.80), but increased the risk with clopidogrel (OR 1.71 (95% CI 1.04 – 2.79), p=0.033 [71]. On the basis of these findings, in selected cases, surgery might be performed after 3 days of

ticagrelor discontinuation.

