4.5.3 In-hospital assessments

The MONET registry does not imply any assessments additional to routine treatment. The following clinical and laboratory variables will be captured by the eCRF:

Clinical characteristics

- Age, gender, body weight.
- Selected coronary risk factors, such as diabetic status, smoking, hypertension, dyslipidemia.

- Cardiovascular status: prior MI, PCI (date of latest stenting), CABG, heart failure, atrial fibrillation, latest left ventricular ejection fraction.

Laboratory tests

- Baseline serum creatinine (eGFR will be automatically calculated by the eCRF using the Cockcroft-Gault formula) and peak serum creatinine during hospital stay.
- Baseline haemoglobin/haematocrit and nadir values during hospital stay.
- CKMB and troponin values should be checked at 6-hour intervals for 24 hours after any suspect ischemic symptoms and/or ischemic ECG changes in the perioperative period, unless otherwise recommended by local practice. The peak value of CKMB will be recorded in the eCRF.

Electrocardiogram

A standard 12-lead ECG will be taken preoperatively, in the case of ischemic symptoms and at discharge.

Concomitant Medications

The following medications will be captured by the eCRF:

- Aspirin
- P2Y₁₂ inhibitors (further subdivided as ticlopidine, clopidogrel, prasugrel, ticagrelor)
- Betablockers
- Statins
- ACEI, ARBS
- Oral anticoagulants (warfarin, acenocumarol, apixaban, dabigatran, edoxaban, rivaroxaban)

- Low-molecular weight heparin
- Tirofiban or eptifibatide
- Cangrelor

The dates and times of perioperative discontinuation and reinstitution (if any) will also be captured.

Drug therapy at discharge and at the 30-day contact will be captured by the eCRF.

Index PCI and surgical procedure details

Details of PCI and surgical procedures will be obtained from interrogation of the medical records and hospital charts.

The delay from stenting to surgery and the type of stent (BMS, first or second generation DES), stent number, length and diameter will be recorded. Surgeries will risk-stratified according to the American College of Cardiology/American Heart Association classification [11]. Moreover, the American Society of Anaesthesiologists (ASA) physical status will be assessed for each patient [21].

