6.6 Delay in performing non cardiac surgical procedure

The delay in performing cardiac and non cardiac surgical procedures will be defined as the time from the time of surgical indication to the time of surgical procedure.

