7. STATISTICS

7.1 The Number of Participants

Consecutive patients will be enrolled over one year of time at the participating Centers.

Cases and controls patients will be divided into those who will use Consensus Document “Stent and Surgery-2” (group 1) vs those who traditionally will be managed by local practice (group 2). On the basis of previous data reported SAS, a sample size of 1623 patients would be required to have a case-control matching 1:2, assuming a study power of 80% and 5% significance. Of those, 324 case-patients (20% of group 1) vs 162 control-patients (ratio 1:2) would be required for enrollment within one-year after implanted stents. Two preplanned interim analyses will be performed by an independent statistician when 800 and 1500 of patients will be enrolled.

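### The 0-3 month timing band hides the one-month threshold, so a shift of surgery from the first month into months 1-3 cannot be seen

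*Combined protocol and SAP*

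**What the plan says.** The timing endpoint appears twice in section 4.3, once per surgery type: "Rate of non cardiac surgical procedures within 12 months from PCI divided into quartiles (0-3, 3-6, 6-9, 9-12 months") and "Rate of cardiac surgical procedures within 12 months from PCI divided into quartiles (0-3, 3-6, 6-9, 9-12 months"). Section 6.5 repeats the bands: "Time from PCI to surgery will be divided into 4 quartiles: from 0 to 3 months, from 3 to 6 months", then 6-9 and 9-12 months.

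Section 2 summarises the timing guidance: "if surgery cannot be delayed, it should be performed after the first month and ideally after at least 3 months from PCI".

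Three other places bear on the point:

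- Section 4.5.3 has the eCRF record "The delay from stenting to surgery and the type of stent", so the interval is held for each patient.
- Section 6.6 defines a separate delay endpoint as "the time from the time of surgical indication to the time of surgical procedure".
- Section 7.2 gives a general rule for categorical data: "Categorical variables will be presented as counts and percentages and will be compared using the chi-square" or Fisher's exact test. It names no test for the timing endpoint, and section 6.5 says only that the rate will be assessed.

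**The concern.** The registry compares centres that follow the consensus document with centres that do not. When surgery takes place after stenting is one of the things the document may change, and the protocol's summary of it sets a minimum (after the first month) and an ideal (three months or later). The endpoint keeps the ideal and loses the minimum: an operation at 2 weeks and one at 11 weeks are counted alike.

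If group 1 centres mainly move early operations from the first month into the following two, the planned table would show no difference between groups, and a reader could take that as no effect on timing. A first-month analysis added after the data are seen would be a post hoc cut-point.

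There are two smaller defects in the same wording. Fixed three-month bands are not quartiles. Adjacent bands also share their limits at 3, 6 and 9 months, with no rule for an operation on the boundary.

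**Working it through.** The plan gives no expected timing distribution, so there is no figure of its own to reproduce. The endpoint is read here as the distribution of timing among patients operated on within 12 months.

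**1. Set the thresholds against the band edges.**

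| Source | Cut-points after PCI (months) |
|---|---|
| Timing guidance, section 2 | 1 and 3 |
| Primary endpoint, sections 4.2 and 6.1 | 3 and 6 |
| Timing bands, sections 4.3 and 6.5 | 3, 6, 9 and 12 |

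Only the one-month point has no matching edge.

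**2. What a shift does to the bands.** Let *a* be the count in month 0-1 and *b* the count in months 1-3. The first band holds *a* + *b*. Moving *m* operations from the first part to the second gives (*a* − *m*) + (*b* + *m*) = *a* + *b*, so the change is zero for any counts.

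An illustration on assumed counts uses 162 operations: 20 in month 0-1, 30 in months 1-3, then 38, 37 and 37. All 20 first-month operations are moved later.

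| Share of the 20 landing in months 3-6 | 0-3 band | Separate 0-1 band |
|---|---|---|
| Before the move | 50/162 = 30.9% | 20/162 = 12.3% |
| 0% | 50/162 = 30.9% | 0% |
| 25% | 45/162 = 27.8% | 0% |
| 50% | 40/162 = 24.7% | 0% |
| 100% | 30/162 = 18.5% | 0% |

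The existing band responds only to operations that cross three months.

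**3. What a first-month comparison could detect.** All rates here are assumptions. Section 7.1 uses a 20% share within one year: 0.20 × 1,623 = 324.6. Split 1:2, this is about 108 in group 1 and 216 in group 2. Uniform timing would put 108/12 = 9 group 1 patients in the first month, or 8.3%. Power at two-sided 5%, unadjusted, by exact binomial enumeration (the lower figure is Fisher, the higher is chi-square without continuity correction):

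| First-month share, group 1 vs group 2 | Power |
|---|---|
| 3% vs 12% | about 80-83% |
| 3% vs 10% | about 61-65% |
| 4% vs 8.3% | about 25-28% |
| 5% vs 8.3% | about 14-17% |

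For 3% vs 10% the 95% half-width of the difference is 1.96 × √(0.03 × 0.97/108 + 0.10 × 0.90/216) = 5.1 percentage points.

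**4. The four-band chi-square and ordered tests in the same setting.** Band probabilities were (*a*, 0.28 − *a*, 0.24, 0.24, 0.24), with timing uniform within bands and *a* = 3% against 10% or 12%. The four-band chi-square rejects in about 5% of samples. That follows from the set-up, because the 0-3 share is 28% in both groups. A Wilcoxon test on the interval rejects in about 6%, and a trend test over bands with a separate first month in about 7-11%. Neither gives useful power for this shift.

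**The case against.** A reader might infer that moving surgery out of the first month cannot alter the timing endpoint at all. The documents do not support that. The same guidance sentence gives three months as the ideal, and three months is a band edge, so operations moved past it do change the bands, as do operations moved past 12 months.

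The chosen edges also have a rationale: 3 and 6 months are the primary endpoint's cut-points. The one-month point appears in general background guidance, and the consensus document itself is not in the text reviewed, so the threshold rests on the protocol's summary of it. These points stand. They make the split a refinement of the bands and give no reason to replace the existing edges.

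A reader might also conclude that the fault lies in an unordered test and that a trend or Wilcoxon test would cure it. Step 4 shows that it would not. That the bands will be compared by chi-square is itself an inference from a general sentence in section 7.2.

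It can fairly be said that the interval is recorded, so a first-month share could be derived at any time. That is true; what is missing is prespecification. The delay endpoint does not supply it, because it runs from surgical indication and is not anchored to PCI.

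**Conclusion.** The concern holds in a limited form. The bands can show movement of surgery past three months but not from the first month into months 1-3, although the protocol names both thresholds. The loss for that shift is complete and depends on no assumption about rates.

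How much the split would gain does depend on assumptions. The 108 vs 216 split is one reading of section 7.1, which calls 324 patients 20% of group 1 although it is 20% of the total 1,623, and sets them against 162 controls. With 162 vs 324 or 324 vs 162, power for 3% vs 10% rises to about 83-88%. Smaller differences remain poorly detected at 108 vs 216, and section 4.3 separates cardiac from non-cardiac surgery, which lowers power further in each.

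This affects one kind of secondary endpoint among the twelve items in section 4.3. It is worth changing because the change is cheap. It does not affect the primary endpoint.

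**What to change.** In sections 4.3 and 6.5:

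- Call the bands intervals, not quartiles, and make them non-overlapping: 0-1, >1-3, >3-6, >6-9 and >9-12 months. This keeps the existing 3-, 6- and 9-month edges.
- Prespecify the share operated on in the first month, by group, with a 95% confidence interval for the difference, separately for cardiac and non-cardiac surgery.

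In section 7.2, name a direct two-group comparison of that share (Fisher or chi-square). An ordered test on the interval may be added to describe a general shift, but it does not replace this comparison.

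The cost is wording only, as the interval is already captured and no visit or variable is added. The drawback is small first-month counts, about 9 of 108 in group 1 if timing were uniform and fewer within each surgery type. The result should therefore be presented mainly as an estimate with its interval, and a non-significant difference should not be read as no effect.
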